| | 
intervention arm) or against a composite reference standard that includes bacteriologically confirmation or/and clinical evidence resulting in therapy initiation.
 
 Diagnostic accuracy of CRP in blood compared to TB symptom's screening in those with microbiologically confirmed TB. 
Comparison of primary and secondary endpoints of the intervention arm with the local standard of care at the sites before the study initiation (a retrospective data collection from consecutive PLHIV admitted at participating hospitals).
 
Sub-analysis
 
 Primary endpoint will be calculated at different intermediate timepoints (48 hours, 7 days and 14 days from enrolment). Primary and selected secondary endpoints will be calculated for participants' subgroups including CD4 cells/mm³ ≥200, <200 and <100, among participants with any TB symptoms, severely ill participants or with AHD, and among participants providing at least one sputum and (or) one urine sample for testing. | | | | | | | | | | | | | | | | | | | | |
| Study Timeline | 
  
 Estimated period for ethics clearance	May / 2022	
 
 Import permits and importation	Jan-May / 2022	
 
 Kick off / training meeting	Nov / 2021	
 
 Estimated date of first participant enrolled:	Sep/ 2022	
 
 Estimated date of last participant enrolled:	Jan/ 2024	
 
 Estimated date of last participant completed:	Mar/ 2024	
 
 Estimated date for end of data cleaning:	May / 2024	
 
 Estimated date for end of data analysis:	July / 2024	
 
 Estimated date for first manuscript draft:	Sep / 2024	
 
 Total duration of study:	47 months	
  
 | Estimated period for ethics clearance | May / 2022 | Import permits and importation | Jan-May / 2022 | Kick off / training meeting | Nov / 2021 | Estimated date of first participant enrolled: | Sep/ 2022 | Estimated date of last participant enrolled: | Jan/ 2024 | Estimated date of last participant completed: | Mar/ 2024 | Estimated date for end of data cleaning: | May / 2024 | Estimated date for end of data analysis: | July / 2024 | Estimated date for first manuscript draft: | Sep / 2024 | Total duration of study: | 47 months |

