10.9 Arm-specific procedures (See table 2)

10.9.1 Intervention arm

The intervention arm for this trial will consist of testing sputum, stool and urine with Ultra and urine with AlereLAM in all recruited patients regardless of symptoms. Thus, all patients allocated to this arm will be asked to provide urine, stool and/or sputum.

This project is part of the EDCTP2 programme supported by the European Union

If urine or sputum cannot be provided spontaneously at the time of recruitment, participants will be asked to do so within 72 hours (aim: within 24 hours from enrolment). Patients will be encouraged to drink water to stimulate diuresis (unless contraindicated). Urine will be collected in specific containers and stored for future testing. Ultra on Stool will be performed in fresh specimen according to the KNCV SOS method³³.

Additionally, we will ask for stool and oral swabs specimen for Xpert Ultra/ LumiraDx testing.

We aim to collect all samples specified for each intervention (including those for exploratory studies) within 72 hours from enrolment. Efforts will be made to collect all samples within the first 24 hours. Time of sample collection will be specified in the sample collection log and CRF.

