10.9.2 Control Arm

The control arm screening and testing strategy will consist of:

Sputum Ultra whenever the patient has cough, fever, weight loss or night sweats and/or *Ultra on any tissue* (including lymph nodes) from patients with suspected extrapulmonary TB.

Urine Alere TB-LAM, if patients 1) have signs and symptoms of TB (pulmonary and/or extrapulmonary), or 2) have advanced HIV disease* or 3) are seriously ill**. The latter two are all irrespective of signs and symptoms of TB.

*Adult patients with advanced HIV disease are those with CD4 cell count <200 cells/mm³ or a WHO clinical stage 3 or 4 event at presentation to the clinic.

**A seriously ill patient is any individual with HIV or of unknown HIV status presenting with one or more of the following danger signs:

- Unable to walk unaided
- A respiratory rate over 30/min
- A fever of more than 39°C, and/or
- A pulse rate of over 120/min

Thus, sputum and urine collection will only be conducted for Ultra and AlereLAM testing if the above-mentioned symptoms/criteria are present. Otherwise, urine alone will be collected in specific containers and stored for future testing. Patients will be encouraged to drink water to stimulate diuresis (unless contraindicated).

The control arm for this trial follows WHO recommendations (as of January 2020) for bacteriological testing among hospitalized HIV-positive individuals.

This project is part of the EDCTP2 programme supported by the European Union

Study staff will collect the samples for both arms.

In case any sample cannot be obtained within the first 72 hours from enrolment, reasons should be recorded in the appropriate CRF. In case the participant can provide the required sample(s) after 72 hours from enrolment, samples should still be collected and processed with clear indication of date and time. Special measures need to be implemented locally so the laboratory is aware of the tests to be performed despite some potential delay in specimen testing. After 72 hours from enrolment have passed, patient will be managed as per national guidelines.

Other than TB, patient clinical management will follow established national guidelines and protocols for hospitalized HIV-positive patients.

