| TB Investigations | | Sputum Ultra | | | | | |
| | Urine | Stool | | | | | |
| | AlereLAM# | Ultra | | | | | |
| | Sputum Ultra* | Urine Ultra | | | | | |
| Samples collected and tests | Blood CD4 | Urine AlereLAM | | | | | |
| | | 2x Oral Swabs | | | | | |
| | | Urine FujiLAM | | | | | |
| | | Blood CD4 | | | | | |
| | | Blood for CRP | | | | | |
| Results issued | | | | X | | | |
| Further contacts | | | | | | | |
| Verification TB diagnosis / ad hoc TB investigations | | | | X | X | X | X |
| Verification TB treatment initiation | | | | X | X | X | X |
| Verification vital status | | | | X | X | X | X |
| HIV care / ART | | | | X | X | X | X |

*Sputum Ultra whenever the patient has cough, fever, weight loss or night sweats and/or Ultra on any tissue (including lymph nodes) from patients with suspected extrapulmonary TB

#Urine LAM if patients have currently signs and symptoms of TB (pulmonary and/or extrapulmonary), or with advanced HIV disease (1) or who are seriously ill (2) or else irrespective of signs and symptoms of TB and with a CD4 cell count of less than 200 cells/mm³.

[&]CD4 count testing will be done if not available within the last 3 months. Most recent viral load will be captured (if available)

**urine should be collected in all participants in the control arm, irrespective of whether LAM test is done.

This project is part of the EDCTP2 programme supported by the European Union

12. Laboratory procedures and storage of samples

Samples will be processed and results issued back to attending physicians as soon as possible. AlereLAM results should be available within two hours from specimen collection. Ultra results should be provided within 24 hours from being collected at the participating hospital laboratory associated facilities.

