13.1 Sample Size calculations

Recent studies using Alere LAM and sputum Xpert to screen unselected admitted HIV positive patients in Southern Africa^{24,29,31} show that around 17% of these patients are laboratory confirmed for tuberculosis. The added yield of using Xpert Ultra instead of Xpert would involve an 11-17%⁴³⁻⁴⁵ relative increase in bacteriological confirmation. Thus, universal AlereLAM testing and sputum Ultra would likely confirm around 20% of unselected admitted HIV participants in our study. We estimate that the bacteriological confirmation in our control arm would be slightly lower than 20%, around 19%, given that we will not use a universal screening strategy but the WHO recommendations (sputum Ultra if TB compatible symptoms and AlereLAM testing if TB compatible symptoms or in those with advanced HIV disease, or seriously ill, or with a CD4 cell count of less than 200 cells/mm³). Based on existing literature, we estimated that up to 10% of participants in our control arm would not receive either Xpert Ultra or LAM testing.

We estimated that the intervention arm would yield around 26% of bacteriologically confirmed cases by universal testing (irrespective of symptoms) with AlereLAM and Xpert Ultra on sputum, urine, and stool. As mentioned before, universal AlereLAM and sputum Xpert Ultra would yield around 20% of bacteriological confirmation. Studies show that Xpert urine could increase bacteriological confirmation by 4%. Although there is limited evidence on the potential benefits of stool Xpert Ultra in adults, there are promising results observed in children (who, as HIV positive patients, often have extrapulmonary TB). Thus, we assume that adding stool Xpert could increase our bacteriological confirmation about 1%. If we apply a similar gain (observed in sputum) in urine and stool by substituting Xpert by Ultra, the combined added yield would be of around 6%. Thus, we expect to have a 26% bacteriological confirmation in our intervention arm by using universal LAM testing and Xpert Ultra on sputum, stool and urine. This would translate into a 7% difference (19-26%) between our control and intervention arm.

The estimation of the bacteriologically confirmed cases in both the control and intervention arm could have the following limitations:

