13.2.3 Pre-specified sub-analysis

- Primary and selected secondary endpoints among PLHIV with ≥ 200 CD4, < 200 CD4 and < 100 CD4 cells/mm³ and
- Primary and selected secondary endpoints among admitted HIV positive patients providing at least one sputum, stool and (or) one urine sample for testing.
- The primary and selected secondary endpoints will also be calculated among those who had their test result available and were started on treatment within 72h of enrolment in both arms (as in a classical per-protocol (PP) analysis).

Both the main clinical trial analyses (related to primary and secondary objectives) and that related to the exploratory objectives (oral swab Ultra and LumiraDx and urine FujiLAM sub-studies) will be expanded in separate statistical analysis plans.

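### The specimen-provider sub-analysis in Protocol 13.2.3 selects participants by different rules in the two arms and, unless stored urine counts, enriches the control subset for TB

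*Protocol*

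**What the plan says.** Protocol 13.2.3 lists, among its pre-specified sub-analyses, "Primary and selected secondary endpoints among admitted HIV positive patients providing at least one sputum, stool and (or) one urine sample for testing". The synopsis has a shorter version without stool: "among participants providing at least one sputum and (or) one urine sample for testing". Neither defines what counts as a sample for testing, and neither attaches a caveat or adjustment.

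The arms differ in who is asked for specimens.

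- **Intervention (10.9.1):** "all patients allocated to this arm will be asked to provide urine, stool and/or sputum", regardless of symptoms.
- **Control (10.9.2):** "sputum and urine collection will only be conducted for Ultra and AlereLAM testing if the above-mentioned symptoms/criteria are present". Sputum Ultra needs cough, fever, weight loss or night sweats. Urine AlereLAM needs TB signs or symptoms, or that patients "have advanced HIV disease* or 3) are seriously ill". Advanced HIV disease means CD4 below 200 or WHO stage 3 or 4. Tissue Ultra is for suspected extrapulmonary TB. No study stool is requested.

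Controls who meet no criterion still give urine, but for storage: "Otherwise, urine alone will be collected in specific containers and stored for future testing". The footnote to the schedule of visits (Table 2) agrees: "urine should be collected in all participants in the control arm, irrespective of whether LAM test is done".

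Protocol 13.1 estimates that "up to 10% of participants in our control arm would not receive either Xpert Ultra or LAM testing". SAP section 9 plans subgroups by country or site, CD4, viral load and sex; it does not mention specimen providers.

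**The concern.** Whether a participant gave a specimen for testing is known only after randomisation. In the intervention arm it depends on ability and willingness; in the control arm it also depends on meeting criteria that predict TB. Restricting both arms to providers therefore leaves two groups that randomisation no longer makes comparable.

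The loss is also informative for the primary endpoint. Confirmation requires a positive test, so a control with no test is almost always a failure. The exceptions are later ad hoc tests (10.10) and the culture route described in 8.1. Dropping such controls removes failures from one arm while every remaining result stays the same. Those dropped are also the patients whom universal testing is meant to reach.

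At stake is a comparison that could be read as the effect among patients who could be tested. On the primary endpoint it would tend to understate the strategy's benefit. On mortality, the retained controls are selected partly on danger signs and advanced disease, so the distortion may favour the intervention.

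**Working it through.** **Inputs.** Planned proportions 19% (control) and 26% (intervention), two-sided alpha 0.05, power 80%, 5% loss, 586 per arm (Protocol 13.1, SAP 5). Untested controls: up to 10% (Protocol 13.1). Subgroup significance level 0.01 (Protocol 13.2.2). The plan gives no figure for the sub-analysis itself.

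**Step 1: reproduce the plan's figure.** With the normal approximation and pooled variance under the null,

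n = [1.96·√(2·0.225·0.775) + 0.8416·√(0.19·0.81 + 0.26·0.74)]² / 0.07² = (1.157 + 0.495)² / 0.0049, which rounds up to 558 per arm.

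558 × 1.05 = 586, the stated number; 558 / 0.95 gives 588. The planning rates are therefore a sound base.

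**Step 2: proportion in the subset.** Let u be the share of an arm with no test specimen. If those participants are in the denominator but not the numerator, removing them changes the proportion from p to p / (1 − u).

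| Controls untested | Intervention without specimen | Control | Intervention | Difference (points) |
|---|---|---|---|---|
| 0% | 0% | 19.0% | 26.0% | 7.0 |
| 5% | 0% | 0.19/0.95 = 20.0% | 26.0% | 6.0 |
| 10% | 0% | 0.19/0.90 = 21.1% | 26.0% | 4.9 |
| 10% | 5% (assumed) | 21.1% | 0.26/0.95 = 27.4% | 6.3 |
| 5% | 5% (assumed) | 20.0% | 27.4% | 7.4 |

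In the last row the loss is equal in both arms: the ratio stays at 1.37 and the difference does not shrink. The shrinkage in the other rows comes from the imbalance between arms. At 10% and 0% the relative increase falls from 36.8% to 0.26/0.211 − 1 = 23.2%.

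**Step 3: no true effect.** With 19% in both arms and 10% of controls untested, the subset shows 19.0 − 21.1 = −2.1 points against the intervention.

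**Step 4: power.** With 586 per arm, power for 19% against 26% is 82% at 0.05 and 62% at 0.01. In the 10%/0% subset (527 controls, 586 intervention; 21.1% against 26%) it is 48% and 25%.

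**Step 5: the other reading.** If stored urine counts as a sample for testing, u is close to zero for controls in the any-specimen subset and the first row applies. A sputum-only comparison would still select controls on symptoms, and a stool-only comparison would have essentially no controls. The documents give no shares from which to size these two.

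**The case against.** The other side has four good points.

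1. **The wording is undefined.** All controls are to give urine, and 10.9.1 uses the same stored-for-future-testing language for intervention urine. On a lenient reading nearly every control qualifies. This stands, and it makes the any-specimen bias conditional. Against it, 10.9.2 contrasts collection for Ultra and AlereLAM with urine that is only stored, so the stricter reading is the more natural one.
2. **The control criteria are wide.** A reader might infer that controls are tested only if symptomatic or severely ill. They are not: advanced HIV disease without symptoms triggers AlereLAM, and suspected extrapulmonary TB triggers tissue Ultra. That breadth is consistent with the small untested share that the protocol expects.
3. **The 4.9 points are near the worst case on the protocol's figures.** Ten per cent is a ceiling, and full provision in the intervention arm is assumed. Some untested controls may have met a criterion but been unable to give a specimen, a loss that would also occur in the other arm.
4. **The analysis is peripheral.** Protocol 13.2 defers details to the SAP, and SAP 9 does not carry this subset. The synopsis also already names a baseline subgroup close to the one needed.

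Points 2 to 4 limit the size and reach of the problem but do not remove it. The protocol still pre-specifies a between-arm comparison in a subset formed differently in each arm, and omission from the SAP leaves it without a definition.

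A reader might also infer that the main efficacy result is biased. It is not: the primary analysis is by intention to treat in all randomised participants.

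**Conclusion.** The concern holds conditionally. If a sample for testing means one tested by Ultra or AlereLAM, the control subset is enriched for TB. The planned 7.0-point difference then becomes 4.9 points at 10% untested controls, 6.0 at 5%, and 6.3 if 10% of controls and 5% of intervention participants give nothing. If stored urine counts, the any-specimen bias largely disappears; sputum-only and stool-only comparisons remain affected.

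The figures assume that untested participants contribute essentially no endpoint successes. They use confirmation rates, whereas the endpoint also requires treatment within 72 hours. Actual proportions may therefore be lower, but the inflation of the control proportion by 1/0.90 is the same.

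A reader might infer a bias of known size on mortality in the opposite direction. The direction is plausible, but the documents give no figure from which to size it. The point is confined to this sub-analysis. It is separate from the per-protocol set and from the specimen-feasibility endpoint.

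**What to change.** - In Protocol 13.2.3 and SAP 9, replace the between-arm specimen-provider comparison with the subgroup that the synopsis already names: any TB symptoms, severely ill, or advanced HIV disease. Fix membership at Day 0, analyse as randomised, and report the complement alongside.
- Take symptoms from the Day 0 screen, which is scheduled in both arms, not from the hospitalisation form in SAP 4.4, which records symptoms after randomisation. CD4 is scheduled at Day 0 and WHO stage is in the baseline form. Confirm that the physical examination at recruitment captures the danger signs in both arms.
- If a specimen-based subset is kept, define it as urine obtained within 72 hours of enrolment in either arm, whether tested or stored. Label it descriptive, and make no between-arm test on sputum or stool provision.
- Align the synopsis, 13.2.3 and SAP 9, including whether stool is listed.

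The cost is mainly wording, since the main baseline items are already collected. There are two drawbacks. The complement would be small (about 10%, taking the untested share as a guide) and imprecise. A urine-based subset also depends on collection in practice, and Protocol 12.5 encourages specimen storage without making it mandatory.

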8.1 Primary Endpoint(s)

The primary endpoint is:

- The proportion of participants diagnosed with microbiologically confirmed TB and started on TB treatment within 72 hours of enrolment, separately for intervention and control arm. The numerator is the number of participants per study arm who are diagnosed with microbiologically confirmed TB and start on treatment within 72 hours of enrolment. The denominator is the number of participants enrolled per study arm. We will compare this indicator between both study arms. Patients are defined to have microbiologically confirmed TB if at least one confirmatory TB test (Ultra, AlereLAM) gives a positive result.

Hospitalized PLHIV experience high mortality and TB underdiagnosis and misdiagnoses are frequent. TB diagnosis is important when you can quickly start appropriate therapy. This endpoint will capture both diagnostic dimensions of the intervention (higher rates of *Mtb* laboratory confirmation) as well as the relevant patient outcome (TB treatment initiated).

Diagnostic procedures and treatment initiation (if appropriate) should be completed within 72 hours of enrolment given the intervention is aimed at rapid collection of samples for all patients upon admission and that Ultra testing can provide results within a few hours from specimen collection at all participating sites.

The numerator of the primary endpoint also includes patients whose bacteriological confirmation might arrive after 72 hours of enrolment. There might be cases where liquid or solid culture might be requested and results arrive after 72 hours. If the patient had been put on treatment empirically (before a positive culture results has arrived), that case will contribute to the numerator, given that treatment would have been started in a "true" TB case.

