10.7 Minimisation of Error and Bias

Selection bias will be minimized by a) the randomization process and b) consecutive enrolment of participants meeting inclusion criteria (and not meeting exclusion criteria). Study staff from all sites will be trained prior to study initiation in order to guarantee that inclusion and exclusion criteria and

This project is part of the EDCTP2 programme supported by the European Union

well understood and applied homogenously across sites.

Other potential sources of bias (ascertainment, information, interpretation), will be also addressed. Laboratory procedures will be standardized across sites, using the same laboratory SOPs and specific lab training, in order to minimize differences by site. Given that most tests are different by arm, and that AlereLAM will be preferably done at the health facility (by the bed side), no blinding of attending physician or lab technologist will be possible. In order to explore the differences between WHO recommended procedures and real standard of care at the sites, there is an exploratory objective aiming at assessing the current yield of TB investigations under routine conditions prior to the study initiation at all sites. This will be consecutive collection of retrospective data from PLHIV admitted at participating hospitals prior the start of the study. The quality and completeness of this data might differ from participating sites.

Decision to start TB treatment will be based on any test results and the criteria of the physician responsible for the patient's care.

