#### 6.1.1 Per Protocol Population

For the primary and some secondary endpoints, we will be using the set of data defined as “per-protocol” (PP). This dataset we will only include participants with all required samples collected and results available within 72 hours from enrolment.

This can shed light on a potential effect of poor adherence to study protocol procedures on the primary and secondary endpoints.

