### 6.2 Missing Data

Given the characteristics and design of the trial (including data monitoring activities) we expect a low proportion of missing variables.

We will analyse the mechanisms that cause missing data. We plan to identify the three typical patterns for missing data: missing completely at random (MCAR); missing at random (MAR); and missing not at random (MNAR).

To assess the potential influence of missing values in intervention related variables or visit related variables (due to withdraws or death), we will compare the results of the ITT and per protocol analyses. To assess the potential influence of missing values in endpoint related

---

variables, we will perform a complete case analysis when the proportion of missing data is below, approximately, 5% and it is implausible that certain patient groups specifically are lost to follow-up in one of the compared arms. In this case we will analyse previously if the missing data are random or follow some pattern.

For missing data over 5%, we will do a worst/best scenario sensitivity analysis for the main endpoint related variables (related TB treatment initiation, time from enrolment and microbiological results). This consists of assigning the best plausible outcome to the above endpoint-related missing values in both arms (i.e TB treatment started, TB treatment started before 72 hours from enrolment, or TB microbiological confirmation) and the other assigning the worst possible outcome to all missing values in both groups (TB treatment not initiated, TB treatment started after 72 hours from enrolment, non-TB microbiological confirmation).

We will also compare the results of one assigning the best possible outcome to missing values in the intervention arm and the worst possible to those of the intervention arm, and vice-versa.

If this sensitivity analyses raise inconsistent results on the intervention effect, their repercussions will be discussed between the statisticians involved in trial analysis.

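### Two supporting rules are wrong as written: the protocol's per-protocol set selects on half of the primary endpoint and conflicts with the SAP's, and the SAP's crossed missing-data scenario never names the control arm.

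*Protocol*

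**What the plan says.** **Primary endpoint.** Protocol 8.1 counts participants with microbiologically confirmed TB who start treatment within 72 hours. On the denominator it says: "The denominator is the number of participants enrolled per study arm". Protocol 13.2.2 scores everyone else as a failure.

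**Per-protocol set.** There are two definitions.
- Protocol 13.2.3 has the primary and selected secondary endpoints "calculated among those who had their test result available and were started on treatment within 72h of enrolment in both arms", and likens this to a classical per-protocol analysis.
- SAP 6.1.1 says: "we will only include participants with all required samples collected and results available within 72 hours from enrolment". It has no treatment condition. Of the comparison with intention-to-treat it says: "This can shed light on a potential effect of poor adherence to study protocol procedures on the primary and secondary endpoints".

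SAP 8.1 and the table shells in SAP 13 report the primary endpoint on the intention-to-treat and per-protocol sets. SAP 7.2 lists a flag for an ATP cohort and does not tie it to either definition.

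**Missing endpoint data.** SAP 6.2 says "we will perform a complete case analysis when the proportion of missing data is below, approximately, 5" per cent, provided that selective loss in one arm is implausible and after a check of the missingness pattern. Above that level: "For missing data over 5%, we will do a worst/best scenario sensitivity analysis for the main endpoint related variables". Two scenarios give both arms the best outcome or both the worst. A further one assigns "the best possible outcome to missing values in the intervention arm and the worst possible to those of the intervention arm", and then the reverse.

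**The concern.** A per-protocol analysis should select on adherence to the assigned testing strategy, not on the outcome. In the protocol's set the treatment half of the endpoint is met by everyone, so only the confirmation half can vary. What is left is the share of early-treated patients who have confirmation. That share falls as more people are treated without confirmation, and Protocol 10.7 leaves this open: "Decision to start TB treatment will be based on any test results and the criteria of the physician responsible". The trial is unblinded and the arms test differently, so the rate of unconfirmed starts may well differ by arm.

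Two current documents also give the same label to different sets. An analyst following the protocol and one following the SAP would report different per-protocol results.

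The missing-data scenarios are meant to show how far missing endpoint values could move the arm difference. Moving both arms the same way hardly changes a difference, so only a crossed scenario bounds it. As worded, that scenario gives the intervention arm two contradictory assignments and the control arm none. At stake is whether a result could be called robust to missing data on the strength of scenarios that could not have shown otherwise.

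**Working it through.** **Inputs.** 19% and 26%, two-sided alpha 0.05, 80% power, 5% loss and 586 per arm come from Protocol 13.1 and SAP 5. The plan treats the confirmation rates as the endpoint rates, and so do I. Rates of early unconfirmed treatment and of missing data are not given; those below are assumptions.

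**The plan's own figure.** The pooled normal formula for 19% against 26% gives 558 per arm. 558 x 1.05 = 585.9, that is 586, as stated (558/0.95 would give 588). Nothing below changes it.

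**Protocol 13.2.3 set.** Let c be the share of enrolled participants who are confirmed and treated within 72 hours. Let e be the share of the rest who have a result and start within 72 hours. The protocol-set proportion is c / (c + e(1 - c)).

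| Scenario | Control | Intervention | Difference |
|---|---|---|---|
| No effect, c = 0.19 in both; e = 0.10 and 0.05 | 0.19/0.271 = 70.1% | 0.19/0.2305 = 82.4% | +12.3 |
| No effect, rates swapped | 82.4% | 70.1% | -12.3 |
| No effect, equal rates | equal | equal | 0 |
| Planned effect, e = 0 in both | 0.19/0.19 = 100% | 0.26/0.26 = 100% | 0 |

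The set can show a difference where there is none, and can show none where the planned 7 points exist.

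**SAP 6.1.1 set.** It has no treatment condition, so none of these figures applies to it. One detail is open: whether a control with no indicated test counts as having all required samples, or as having no result. Protocol 13.1 expects up to 10% of controls to have neither test, but does not say that these are the people without an indication. If 10% of controls, all without events, were dropped and the intervention arm left intact: 19/0.90 = 21.1%, and 26 - 21.1 = +4.9 points. The same rule also drops intervention participants who lack any specimen. If 10% without events were dropped from both arms: 26/0.90 = 28.9%, and 28.9 - 21.1 = +7.8 points. The direction is therefore undetermined.

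**SAP 6.2 scenarios.** Assume 35 of 586 missing per arm (6.0%). Then 551 are observed, with 105 control events (19%) and 143 intervention events (26%). Pooled two-sample z test on 586 per arm:

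| Scenario | Intervention | Control | Difference | p |
|---|---|---|---|---|
| Both worst | 143/586 | 105/586 | +6.5 | 0.007 |
| Both best | 178/586 | 140/586 | +6.5 | 0.013 |
| Crossed, unfavourable | 143/586 | 140/586 | +0.5 | 0.84 |
| Crossed, favourable | 178/586 | 105/586 | +12.5 | <0.001 |

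**Just under the 5% limit.** With 29 missing per arm (4.95%), complete-case analysis gives 145/557 against 106/557, +7.0 points (p = 0.005). The crossed bounds on all 586 are 145/586 - 135/586 = +1.7 (p = 0.49) and 174/586 - 106/586 = +11.6.

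**The case against.** **The SAP already settles the per-protocol set.** Protocol 13.2 leaves the analysis details to the SAP, and the SAP has dropped the treatment-start condition. This stands. A reader might infer that the per-protocol result to be reported is contaminated by outcome selection; the documents do not support that. The 12.3 points arise only if the protocol text is followed, the start rates behind them are assumed, and the sign depends on them. What remains is that the protocol text is current and the SAP does not say that it departs from it.

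**The SAP set needs no rule for untested controls.** On the plain reading, required samples are arm-specific (Protocol 10.9.1 and 10.9.2), so a control with no indicated test lacks nothing. This mostly stands. A reader might also infer that the SAP set dilutes the effect to 4.9 points, but that figure leaves the intervention arm untouched. A clarifying sentence is enough.

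**The repeated arm name is a slip.** The closing reversal and the preceding same-direction scenarios show that a crossed comparison was meant, and a statistician would probably run it correctly. This stands, so the correction is editorial. The text as it is still defines no cross-arm bound.

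**The complete-case rule is conditional.** A reader might take it as an unqualified licence to drop participants. It is not: differential loss must be implausible and the pattern checked first. The unfavourable bound is also extreme by construction, giving every missing control an event when the observed rate is 19%. Wide bounds do not show that the rule is faulty. The rule does still depart from the all-enrolled denominator in Protocol 8.1.

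**Conclusion.** The point holds for two supporting rules. The protocol's per-protocol set conditions on part of the primary endpoint, cannot measure the effect of the testing strategy, and conflicts with the SAP's set. The crossed scenario in SAP 6.2, taken literally, gives no bound across arms. In the example with 35 missing per arm, the scenarios that can be run both stay at +6.5 points while the intended bounds run from +0.5 to +12.5.

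These sizes rest on the planned 19% and 26%, on assumed early-start rates and on assumed equal missingness. The faults in the wording do not depend on those values. The intention-to-treat set, the primary analysis on it and the sample size are not affected. The complete-case rule and the status of untested controls are matters of clarification. Severity is minor.

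**What to change.** 1. **Protocol 13.2.3:** delete the treatment-start condition and use the SAP 6.1.1 set in both documents. State in SAP 7.2 that the ATP flag marks this set.
2. **SAP 6.1.1:** add that required samples are those required in the participant's own arm, so that a control with no indicated test is included. Describe the contrast with intention-to-treat as descriptive, because completeness demands differ by arm. Its use in SAP 6.2 for intervention- and visit-related missingness can stay on that footing.
3. **SAP 6.2:** in the crossed scenario, change the second mention of the intervention arm to the control arm.
4. **Optional:** report the same bounds when missing endpoint data are at or below 5%, so that complete-case results sit beside an all-enrolled analysis.

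The cost is a wording amendment to a protocol that ethics committees review, a short SAP revision and a few lines of code. Symptom screening, CD4, WHO stage and a physical examination are already planned. SAP 4.4 does not list the danger signs or suspected extrapulmonary disease that also trigger control testing, so check that the case report forms record them before relying on item 2. The per-protocol contrast could then no longer be presented as an adherence effect.
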